4. STUDY DESIGN

4.1. Overall design

This is a Phase 1 observer-blind, controlled, self-contained, randomised, single-centre, dose-escalation study with 3 Steps (Step 1a, Step 1b, and Step 2). A total of 96 participants in 7 study groups, including 17 sentinel participants, are planned to be enrolled in the study. [Figure 1](#) shows a visual representation of the study design and [Table 4](#) shows a description of the study intervention groups.

An electronic case report form (eCRF) and a paper Diary will be used for data collection, which will include biological sampling (blood) and safety follow-ups.

The study design, the enrolment, and the monitoring procedures will follow GSK safety standards for FTIH clinical studies (Refer to Sections [8.2.2](#) and [10.1.5](#) for details on staggered vaccination, safety monitoring, and holding rules).

The primary completion date will be at Visit 6 (Day 197), 28 days after administration of the second study intervention (booster vaccination). An extended safety follow-up will be performed until 6 months after this second study intervention administration (Day 337) for collection of SAEs.

Figure 1 Study design overview

[figure not shown]

Table 4 Study groups, intervention, and blinding

Study groups	Number of participants	Age (Min-Max)	Study intervention(s)	Blinding	
				FSFV → IA 1*	IA 1* → LSLV)
Step 1a low dose without Alum	12	18 – 50 years	2 intramuscular vaccinations (Day 1 and Day 169) with low dose of Vi-CRM ₁₉₇ +O:2-CRM ₁₉₇ without Alum	Observer-blind	Single-blind*
Step 1a control	6		1 intramuscular vaccination (Day 1) with TYPHIM VI and 1 intramuscular vaccination (Day 169) with CCI [REDACTED]		
Step 1b low dose with Alum	12		2 intramuscular vaccinations (Day 1 and Day 169) with low dose of ADJ+Vi-CRM ₁₉₇ +O:2-CRM ₁₉₇ with Alum		
Step 1b control	6		1 intramuscular vaccination (Day 1) with TYPHIM VI and 1 intramuscular vaccination (Day 169) with CCI [REDACTED]		
Step 2 full dose without Alum	24		2 intramuscular vaccinations (Day 1 and Day 169) with full dose of Vi-CRM ₁₉₇ +O:2-CRM ₁₉₇ without Alum		
Step 2 full dose with Alum	24		2 intramuscular vaccinations (Day 1 and Day 169) with full dose of ADJ+Vi-CRM ₁₉₇ +O:2-CRM ₁₉₇ with Alum		
Step 2 control	12		1 intramuscular vaccination (Day 1) with TYPHIM VI and 1 intramuscular vaccination (Day 169) with CCI [REDACTED]		

FSFV = first subject first visit; IA = interim analysis; LSLV = last subject last visit

*Refer to Sections 6.3.4 and 9.5.1 for additional details on change of blinding during the interim analysis

4.2. Scientific rationale for study design

4.2.1. Rationale for choice of vaccination route and schedule

Previous clinical studies (CTRI/2018/11/016419, CTRI/2019/07/020451, CTRI/2020/03/023712) with the typhoid component of the Vi-CRM₁₉₇+O:2-CRM₁₉₇ vaccine have shown sufficient immunogenicity and an acceptable safety profile with a single intramuscular injection, which led to the licensing of the vaccine in India.

According to results from preclinical studies in mice [Micoli, 2012; Micoli, 2020] with each component of the Vi-CRM₁₉₇+O:2-CRM₁₉₇ vaccine, 2 injections may be needed in clinical studies to achieve optimal immunogenicity of the paratyphoid A component. An interval of 6 months between 2 vaccinations is expected to boost the immune response from the second vaccination. The selected schedule is considered appropriate for this FTIH study.

4.2.2. Rationale for choice of follow-up period

No adverse events of special interest are planned to be collected in this study; the investigational vaccine does not contain any novel adjuvant and the Vi-CRM₁₉₇ component is already registered in India with no particular safety concern observed during its development (refer to the IB). No particular safety concerns have been identified in other licensed Vi-based vaccines against typhoid fever.

A 6-month follow-up period after the first study intervention administration will allow the identification of any possible late-occurring AEs. A follow-up of 28 days after the second study intervention administration will allow collection of unsolicited AEs and any other event as indicated in [Table 12](#). An extended 6-month safety follow-up after the second study intervention administration will collect any late-occurring SAE and AEs/SAEs leading to withdrawal or study discontinuation.

4.2.3. Rationale for choice of study population

Healthy adults in Europe have been chosen since enteric fever caused by typhoid and paratyphoid A is not endemic in this population. Therefore, it is expected that participants will not have pre-existing antibodies, which may interfere with the immunogenicity evaluation of the candidate vaccine. This study population has also been chosen on the basis of being a low-risk population for the assessment of safety of a FTIH vaccine. The age of participants selected for this study is consistent with planned clinical development of the vaccine.

4.2.4. Rationale for choice of active comparator

The safety profiles of both TYPHIM VI and [CCI](#) [REDACTED] are well characterised. Additionally, both comparator vaccines are not likely to be part of the routine vaccination schedule of study participants, hence, all participants may receive benefit of vaccination by participation in the study.

TYPHIM VI, which is licensed in Europe, has been chosen as a comparator, rather than the TYPHIBEV vaccine (not licensed in Europe) or any other conjugated typhoid vaccines. This is consistent with the primary objective being safety in this FTIH clinical study.

4.3. Justification for dose

The full dose for the typhoid, Vi-CRM₁₉₇ component, to be used in this study is the same as the dose of the monovalent vaccine licensed for protection against typhoid fever among individuals aged 6 months to 45 years in 2020 in India and WHO pre-qualified in the same year. That dose was shown in a Phase 2/3 clinical study (CTRI/2018/11/016419) to be comparable in terms of safety and immunogenicity to a licensed Typhoid Vi-Tetanus Toxoid conjugate vaccine (Typbar-TCV, Bharat Biotech) when administered to healthy adults, children, and infants.

Two injections with the highest dose of the paratyphoid A, O:2-CRM₁₉₇ component to be used in this study have shown a robust immune response in mice, rats, and rabbits.

Results from a repeat-dose toxicology study in rabbits are available in the IB to confirm the safety of the highest antigen doses. There are no clinical safety data with the use of the paratyphoid A component of the vaccine in humans.

Although a 4-fold decrease in antigen was preferred from the full dose to the low dose, a 5-fold decrease has been chosen instead for reasons of practical feasibility of the volume to be administered. Fractional dosing will be used for administration of the low dose due to the lack of a commercially available diluent.

Aluminium Hydroxide (Alum) has been added to this vaccine as an adjuvant to enhance the immune response to the O:2-CRM₁₉₇ component, with the expectation that it will lead to antigen sparing and the use of an effective single-dose vaccine in humans. Adjuvant effects have been shown in animal studies but still need to be confirmed in human studies.

4.4. End of Study definition

A participant is considered to have completed the study if he/she returns for the last Visit or is available for the last scheduled procedure as described in the protocol.

End of Study (EoS): Last Subject Last Visit (safety phone contact, Day 337).

5. STUDY POPULATION

Adherence to the inclusion and exclusion criteria specified in the protocol is essential. Deviations from these criteria are not allowed because they can jeopardise the scientific integrity, regulatory acceptability of the study or safety of the participant.

5.1. Inclusion criteria

All participants must satisfy ALL the following criteria at study entry:

- Participants who, in the opinion of the Investigator, can and will comply with the requirements of the Protocol (e.g., completion of the diary cards, return for follow-up visits).
- Written informed consent obtained from the participant prior to performance of any study specific procedure.
- Healthy participants as established by medical history, clinical examination, and Screening laboratory investigations.
- Participant satisfying Screening requirements.
- Participant seronegative for human immunodeficiency virus, hepatitis B, and hepatitis C at Screening.

- A male or female participant between, and including, 18 and 50 years of age at the time of the first study intervention administration.
- Female participants of non-childbearing potential may be enrolled in the study. Non-childbearing potential is defined as pre-menarche, current bilateral tubal ligation or occlusion, hysterectomy, bilateral ovariectomy or post-menopause. Refer to Section 10.4.1 for definitions of women of childbearing potential, menarche, and menopause.
- Female participants of childbearing potential may be enrolled in the study if the participant:
 - has practiced adequate contraception for 1 month prior to study intervention administration, and
 - has a negative pregnancy test on the day of study intervention administration, and
 - has agreed to continue adequate contraception during the entire treatment period and for 1 month after completion of the study intervention administration series.

5.2. Exclusion criteria

The following criteria should be checked at the time of study entry. The potential participant MUST NOT be included in the study if ANY exclusion criterion applies:

5.2.1. Medical conditions

- Progressive, unstable, or uncontrolled clinical conditions.
- History of any reaction or hypersensitivity likely to be exacerbated by any component of the vaccine.
- Hypersensitivity, including allergy, to medicinal products or medical equipment whose use is foreseen in this study.
- Clinical conditions representing a contraindication to intramuscular vaccination and blood draws.
- Any confirmed or suspected immunosuppressive or immunodeficient condition, based on medical history and physical examination (no laboratory testing required).
- Any behavioural or cognitive impairment or psychiatric disease that, in the opinion of the Investigator, may interfere with the participant's ability to participate in the study.
- Acute* or chronic illness, clinically significant pulmonary, cardiovascular, hepatic, or renal functional abnormality, as determined by physical examination or laboratory screening tests.

*Participants with a minor illness (such as mild diarrhoea or mild upper respiratory infection) without fever may be enrolled at the discretion of the Investigator.

- Any clinically significant* haematological (haemoglobin level, white blood cell, lymphocyte, neutrophil, eosinophil, platelet, red blood cell count and erythrocyte mean corpuscular volume) and/or biochemical (alanine aminotransferase [ALT], aspartate aminotransferase [AST], creatinine, and total protein) laboratory abnormality.
- *The Investigator should use his/her clinical judgement to decide which abnormalities are clinically significant.
- Confirmed positive COVID-19 test during the period starting 14 days before the first administration of study vaccines (Day -14 to Day 1).
- Any other clinical condition that, in the opinion of the Investigator, might pose additional risk to the participant due to participation in the study.
- Confirmed or suspected autoimmune diseases (e.g., vitiligo, autoimmune thyroiditis).

5.2.2. Prior/Concomitant therapy

- Previous administration of any type of Typhoid vaccine (Ty21a, Vi-PS, or Typhoid conjugate vaccine).
- Use of any investigational or non-registered product (drug, vaccine, or medical device) other than the study interventions during the period starting 30 days before the first administration of study vaccines (Day -30 to Day 1), or planned use during the study period.
- A vaccine not foreseen by the study protocol administered during the period starting at -14 days before the first dose (-21 days in the case of live vaccines) and ending 28 days after the last dose of study intervention administration*, with the exception of flu and COVID-19 vaccines, administered during the period starting at 7 days before and 7 days after each dose (14 days before and 14 days after in case of live vaccines).

*In case emergency mass vaccination for an unforeseen public health threat (e.g., a pandemic) is recommended and/or organised by public health authorities outside the routine authorisation programme, the time period described above can be reduced if, necessary for that vaccine, provided it is used according to the local governmental recommendations and that the Sponsor is notified accordingly. When regulations allow, the recommended time intervals for administration of these vaccines are at least 7 days before or 7 days after (at least 14 days before or 14 days after in case of live vaccines) each dose of study intervention administration.

- Administration of long-acting immune-modifying drugs at any time during the study period (e.g., infliximab).
- Administration of immunoglobulins and/or any blood products or plasma derivatives during the period starting 3 months before the administration of the first dose of study intervention or planned administration during the study period.

- Chronic administration (defined as more than 14 days in total) of immunosuppressants or other immune-modifying drugs during the period starting 3 months prior to the first study intervention dose. For corticosteroids, this will mean prednisone equivalent ≥ 20 mg/day for adult participants. Inhaled and topical steroids are allowed.

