1.2. Schema

1.3. Schedule of Activities (SoA)

Table 1 Schedule of Activities (SoA)

Type of contact	Screening period	Visit 1 (Priming Vacc)	Sentinel participant safety phone contact	Reminder phone contact 1	Visit 2	Visit 3	Visit 4 (Booster Vacc)	Reminder phone contact 2	Visit 5	Visit 6	Follow-up safety phone contact
Time points	Day -21 to Day -1	Day 1	Day 2	Day 4	Day 8	Day 29	Day 169	Day 172	Day 176	Day 197	Day 337
Informed consent (Section 10.1.3)	•										
Check of inclusion/exclusion criteria (Sections 5.1 and 5.2)	•	•					•				
Collection of demographic data (Section 8.2.1.1)	•										
Medical history (Section 8.2.1.2)	•										
Physical examination (including vital sign assessment and body temperature measurement) (Section 8.2.1.3)	•	•					•				
Symptom-directed physical examination (Section 8.2.1.3)					○	○			○	○	
Height and weight measurement (Section 8.2.1.3)	•										
Randomisation (Section 6.3)		•									
Study intervention											
Check of contraindications and warnings, and precautions to vaccination (Sections 7.1.1 and 8.2.1.6)	○	○					○				
Check of criteria for temporary delay for enrolment and/or study intervention administration (Section 5.5)	○	○					○				

CONFIDENTIAL

205480 (TYPH-PARATYPH A CONJ VI-CRM O2-CRM GVGH-001 (H02_01TP))
 Protocol Amendment 2 Final

Type of contact	Screening period	Visit 1 (Priming Vacc)	Sentinel participant safety phone contact	Reminder phone contact 1	Visit 2	Visit 3	Visit 4 (Booster Vacc)	Reminder phone contact 2	Visit 5	Visit 6	Follow-up safety phone contact
Time points	Day -21 to Day -1	Day 1	Day 2	Day 4	Day 8	Day 29	Day 169	Day 172	Day 176	Day 197	Day 337
Pregnancy test (Section 8.2.1.4)	● ¹	● ²					● ²				
Study intervention allocation (Section 6.3)		●									
Administration of the Vi-CRM197+O:2-CRM ₁₉₇ vaccine (low or full dose, with or without Alum), or control		● ³					● ⁴				
Laboratory assessments											
Blood sampling for antibody determination (~10 mL)		● ⁵				●	● ⁵		●	●	
Blood collection for assay standard generation (~15 mL)										●	
Blood sampling for safety Screening laboratory assays (refer to Table 17) (~20 mL)	●										
Blood sampling for safety laboratory assays (haematological and clinical chemistry analyses) (~13.5 mL)		● ^{5,6}			●		● ⁵		●		
Safety assessments											
Recording of any concomitant medication/vaccination (Section 6.8)	●	●	● ⁷		●	●	●		●	●	
Recording of any intercurrent medical conditions (Section 9.3.1)		●	● ⁷		●	●	●		●	●	

CONFIDENTIAL

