⁶If a blood sample has been collected during Screening in the 3 days before the date of first vaccination, another safety blood sample does not need to be collected on Visit 1.

⁷All information needs to be verified at the site during an *ad hoc* Visit. Refer to Section 8.2.2 for details on safety monitoring.

AE=adverse event; eCRF=electronic case report form; SAE=serious adverse event; VACC=vaccination

Note: The double-line border following Day 29 and Day 197 indicates the interim analyses, which will be performed on all data obtained up to Day 29 (28 days after first vaccination in Step 2) and Day 197 (28 days after second vaccination in Step 2). The double-line borders following Day 337 indicate the final analysis in these participants, which will be performed on all data obtained up to Day 337.

● is used to indicate a study procedure that requires documentation in the individual eCRF.

○ is used to indicate a study procedure that does not require documentation in the individual eCRF.

Table 2 **Intervals between study visits**

Interval	Planned Visit interval	Allowed interval range
Visit 1 → Visit 2	7 days	7 days – 10 days
Visit 1 → Visit 3	28 days	28 days – 33 days
Visit 1 → Visit 4	168 days	158 days – 178 days
Visit 4 → Visit 5	7 days	7 days – 10 days
Visit 4 → Reminder phone call 2	3 days	1 day – 3 days
Visit 4 → Visit 6	28 days	28 days – 33 days
Visit 4 → Follow-up safety phone contact	168 days	154 days – 182 days

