5.5. Criteria for temporarily delaying study intervention administration

Study intervention administration may be postponed within the permitted time interval until transient conditions cited below are resolved:

- Participants with haematological/biochemical values out of normal range which are expected to be temporary may be rescreened/re-vaccinated at a later date, within the allowed time interval.
- Acute disease and/or fever at the time and/or study intervention administration. Refer to the SoA (Section 1.3) for definition of fever and preferred location for measuring temperature in this study.
- Participants with a minor illness (such as mild diarrhoea, mild upper respiratory infection) without fever may be dosed at the discretion of the Investigator.
- Participants with a positive COVID-19 test before a planned study intervention administration will be allowed to receive the study intervention only if at least 14 days have passed since the first positive test.
- Participants receiving flu and COVID-19 vaccines, administered during the period starting at 7 days before and 7 days after each planned dose (14 days before and 14 days after in case of live vaccines).
- Use of antipyretics and/or analgesics and/or antibiotics within 3 days prior to study intervention administration.

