7.1.1. Contraindications to subsequent study intervention(s) administration

The eligibility for subsequent study intervention administration must be confirmed before administering any additional dose.

Participants who meet any of the criteria listed below or criteria listed in sections [5.2.1](#) and [5.2.2](#) should not receive additional doses of study intervention. Such participants should be encouraged to continue other study procedures, at the investigators' discretion (Section [10.3.8.2](#)). All relevant criteria for discontinuation of study intervention administration must be recorded in the eCRF.

- Participants who experience any SAE judged to be possibly or probably related to study intervention or non-study concomitant vaccine/product, including hypersensitivity reactions.
- Participants who develop any new condition which, in the opinion of the Investigator, may pose additional risk to the participant if he/she continues to participate in the study.
- Any condition that in the judgement of the Investigator would make intramuscular injection unsafe.

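### Read literally, the flu/COVID-19 exception in 5.2.2 exempts vaccines given close to a dose and excludes them on other days, contrary to 5.5; the literal rule would stop dose 2 after a routine mid-interval vaccine

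*Protocol*

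**What the plan says.** **Protocol 5.2.2** bars vaccines outside the protocol from 14 days before the first dose (21 if live) until 28 days after the last dose, "with the exception of flu and COVID-19 vaccines, administered during the period starting at 7 days before and 7 days after each dose". For live vaccines the bracketed window is 14 days either side. A footnote, limited to emergency mass vaccination, lets the period be shortened and adds that "the recommended time intervals for administration of these vaccines are at least 7 days before or 7 days after" each dose (14 if live).

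**Protocol 5.5** opens with "Study intervention administration may be postponed within the permitted time interval until transient conditions cited below are resolved" and lists among those conditions: "Participants receiving flu and COVID-19 vaccines, administered during the period starting at 7 days before and 7 days after each planned dose", again with 14 days for live vaccines.

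**Reach of 5.2.2.** The introduction to 5.2 says: "The potential participant MUST NOT be included in the study if ANY exclusion criterion applies". That sentence concerns study entry, but the Schedule of Activities marks the inclusion/exclusion check at Screening, Visit 1 and Visit 4. Section 7.1.1 then covers "Participants who meet any of the criteria listed below or criteria listed in sections" 5.2.1 and 5.2.2, and says such participants should not be dosed again.

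**Timing.** Table 2 allows "158 days – 178 days" from Visit 1 to Visit 4. Table 6 widens this to 154-182 days under special circumstances.

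**Analysis.** Protocol 9.3.1 says participants who meet 7.1.1 criteria, or who use foreseen vaccines outside a recommended window that it does not define, may be eliminated from the per-protocol analysis. It refers further criteria to the SAP and the Protocol Deviation Management Plan.

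**The concern.** An exception to an exclusion describes what is allowed. In 5.2.2 what is allowed, taken literally, is a flu or COVID-19 vaccine within 7 days of a dose, which is the period in which one would least want it. The same vaccine in the middle of the 24-week interval falls back under the general exclusion. Section 5.5 treats the near-dose window in the opposite way.

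This is an operative rule, and the protocol leaves little room to apply it by intent. Section 5 does not permit deviations from eligibility criteria, section 8 restricts waivers to immediate safety concerns, and the glossary ties eligibility to strict adherence. A site that follows the words would withhold dose 2 after an ordinary seasonal flu vaccine. A site that follows the evident purpose would give it. Participants who discontinue are not replaced (7.1) and groups number 6 to 24, so the rule should have a single reading.

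**Working it through.** The plan gives no figure to reproduce. The check sets 5.2.2 beside 5.5 and counts days.

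**Inputs.** Doses on Day 1 and Day 169, with no Day 0 (SAP 6.4). General exclusion from 14 days before dose 1 to 28 days after dose 2, and window of 7 days either side of each dose (5.2.2, non-live). Visit 4 at 158-178 days (Table 2) or 154-182 days (Table 6) after Visit 1. Let v be the vaccine day and d the dose-2 day. Exactly 7 days is first taken as inside the window in both sections.

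**1. Literal 5.2.2 on the planned schedule, non-live.**
- Whole period: 14 + 168 + 28 + 1 = 211 days.
- Exempt: Day -7 to Day 8 and Days 162-176, 15 + 15 = 30 days.
- Still excluded: 211 - 30 = 181 days, made up of Days -14 to -8 (7), Days 9-161 (153) and Days 177-197 (21).
- For live vaccines the mid-interval excluded days are Days 16-154, which is 139 days.

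Before dose 1, a vaccine 8-14 days earlier excludes the participant and one 1-7 days earlier does not.

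**2. Dose 2 after a mid-interval vaccine.** For v ≥ 9, the vaccine is exempt only if |d - v| ≤ 7.

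| Visit 4 window | Permitted dose-2 days | Latest v never exempt | Vaccine days that would stop dose 2 on every permitted day |
|---|---|---|---|
| Table 2 | Days 159-179 (21) | 159 - 8 = 151 | Days 9-151 = 143 |
| Table 6 | Days 155-183 (29) | 155 - 8 = 147 | Days 9-147 = 139 |

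Example: v = 100 leaves 0 of 21 permitted days open under the literal text. An avoidance rule, |d - v| > 7, leaves 21 of 21.

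**3. 5.2.2 against 5.5.** For a vaccine between the doses and more than 7 days after dose 1, literal 5.2.2 requires |d - v| ≤ 7 and 5.5 requires |d - v| > 7. No day satisfies both. With dose 2 planned for Day 169 and v on Days 162-168, 5.5 moves the dose to v + 8, that is Days 170-176, all within Table 2. The vaccine is then 8 days before dose 2 and no longer exempt: 7 of 7 vaccine days. For v = 165, dosing on Day 169 is exempt under 5.2.2; moving to Day 173 to satisfy 5.5 makes the participant excluded.

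**4. Boundary.** The footnote accepts a gap of exactly 7 days, whereas the bracketed windows appear to include it. If exactly 7 days counts as outside the window in both sections, the Table 2 range in step 2 becomes Days 8-152 (145 days). The conclusion is the same, but the text should settle the point.

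**5. Would rewording 5.2.2 alone be enough?** No. Under a plain avoidance rule, a vaccine on Days 1-8, after dose 1, would meet 5.2.2. Through 7.1.1 it would then stop dose 2 on all 21 permitted days, with no postponement able to cure it. Section 7.1.1 needs a matching sentence.

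**The case against.** The strongest reply is that the clause is ambiguous rather than reversed. The comma before its second half, and phrasing that mirrors the main clause, let it be read as substituting a shorter exclusion period for flu and COVID-19 vaccines. A wider window for live vaccines makes sense only as avoidance, 5.5 treats the window as a reason to delay, and the footnote recommends spacing. A single site would probably apply that reading. This largely stands as evidence of intent. It does not settle the wording, and the footnote does not cover routine flu vaccination.

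The force of the text is also softer than an absolute bar. The mandatory sentence in 5.2 is about entry, 7.1.1 is advisory in form, 5.5 permits rather than requires postponement, and per-protocol elimination is discretionary. The Protocol Deviation Management Plan, not among the documents, may already define the window in 9.3.1. These points stand and limit the severity.

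A reader might infer that the protocol deliberately permits co-vaccination next to a dose, or that dose-2 exposure, solicited-event rates or the per-protocol set will suffer. The documents support neither inference. Section 5.5 contradicts the first. For the second, no co-vaccination rate is given and SAP 11.2 decides exclusions case by case.

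**Conclusion.** The clause is wrong as written, with minor operational severity. Taken literally it contradicts 5.5 and, through the Visit 4 check and 7.1.1, gives the wrong answer for dose 2 after a non-live flu or COVID-19 vaccine on Days 9-151 (143 days, Table 2) or Days 9-147 (139 days, Table 6). The counts assume dose 1 on Day 1, the literal reading, exactly 7 days inside the window, and no shortening under the emergency-vaccination footnote. They measure how much of the calendar the wording covers, not how many participants would be affected. No endpoint, sample size or analysis method changes.

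**What to change.** - **5.2.2:** keep the reference to flu and COVID-19 vaccines as the exception and replace the rest of the clause with: *which are allowed except during the period from 7 days before to 7 days after each dose (14 days before to 14 days after in case of live vaccines)*.
- **7.1.1:** add that, for these vaccines, only the interval to the upcoming dose is assessed. A vaccine inside that window leads to postponement under 5.5. A vaccine given soon after dose 1 is recorded as a deviation and does not by itself prevent dose 2.
- **Boundary:** state whether exactly 7 (or 14) days is inside the window, so that 5.2.2, 5.5 and the footnote agree.
- **9.3.1 and the Protocol Deviation Management Plan:** use the same definition for the recommended window.

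The cost is one reworded clause, one added sentence or two, and aligned cross-references. No new procedure is needed, because 6.8 already records vaccinations from Day -30 to Day 197. Rewording cannot prevent an unplanned vaccine soon after a dose, but it makes the handling of one unambiguous.
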